### 5.6. Study Drug Accountability

Study drug and bottles must be returned to the investigator at each visit. The investigator is responsible for study drug accountability, reconciliation, and record maintenance. In accordance with all applicable regulatory requirements, the investigator or designated study center personnel must maintain study drug accountability records throughout the study. The investigator will return all unused study drug to the sponsor or sponsor's designee.

Study drug accountability forms maintained during the study will be used to support subject dosing data. Study center personnel are responsible for reconciling and resolving discrepancies in study drug accountability. It is the responsibility of the Sponsor study monitor (or designee) to periodically review study drug accountability records to ensure that FDA regulations and guidelines concerning study drug accountability are being adhered to.

Periodic inventories of study drug during the study and at the end of the study will be performed by the Sponsor study monitor (or designee) and the investigator (or designee). Missing study drug must be recorded on the study drug accountability/return forms along with an explanation of the discrepancy. Missing medication stock must be reported to the Sponsor immediately when discovered. It is essential that all study drug be accounted for. All unused study drug and bottles will be returned to Pfizer or designee, after the proper completion of Drug Enforcement Agency (DEA) 222 forms.

### 5.6.1. Destruction of Study Drug Supplies

Final Protocol Amendment 2, 26 May 2015

The sponsor or designee will provide guidance on the destruction of unused study drug (eg, at the site). If destruction is authorized to take place at the study site, the investigator must ensure that the materials are destroyed in compliance with applicable environmental regulations, institutional policy, and any special instructions provided by Pfizer, and all destruction must be adequately documented.

### 5.7. Concomitant Medication(s)

# 5.7.1. Permitted Medications and Therapies

Permitted medications and therapies during this study will include:

- Acetaminophen and/or NSAID's (as a rescue medication) anytime during the Treatment and Post-Treatment Periods.
- IR morphine as a single ingredient product at usual doses as rescue medication during the Conversion/Titration Phase until a stable dose is achieved. IR morphine for rescue is discouraged during the Maintenance Phase.
- Non-opioid adjunctive analgesics, bowel regimens, and anti-emetics are permitted.
- For any other medications and therapies not listed (eg but not limited to CNS depressants including sedatives, hypnotics, and other tranquilizer-type drugs (eg, benzodiazepines, phenothiazines) the investigator will consult with Pfizer's clinical team because of the risk of hypotension, respiratory depression, and profound sedation or coma.
- Other non-scheduled prescribed medications for treatment of concomitant medical conditions (eg, cancer, arthritis, diabetes).
- Any drug deemed necessary to either treat opioid toxicity (eg, vasopressors, naloxone) or control signs and symptoms of opioid withdrawal (eg, midazolam, ondansetron).
- Stable regimen of prescribed physical therapy, including heat application (at the same intensity and frequency as at study entry).

### 5.7.2. Prohibited Medications and Therapies

- Opioid analgesics (including tramadol, tapentadol, buprenorphine), except IR morphine as rescue medication during the Conversion/Titration and Maintenance Phases. This includes mixed agonist/antagonist opioid analgesics (eg, pentazocine, butorphanol).
- Monoamine oxidase inhibitors.
- Ethanol in the form of alcoholic beverages (includes medications containing alcohol).

#### **5.8. Rescue Medication**

Subjects/caregivers will be required to record use of rescue medication in the diary during the Treatment Period and Post-Treatment Period.

Acetaminophen and/or NSAID medications (eg, ibuprofen) as allowed by label for children/adolescents is permitted as rescue medication, at the discretion of the investigator, at any time in conjunction with PF-06412528 to provide pain relief. The use of IR morphine as a rescue medication is permitted during the Conversion/Titration Phase, at the discretion of the investigator, to aid in the conversion.

### 6. STUDY PROCEDURES

Subjects/caregivers will be asked to complete a diary each day during the Treatment and Post-Treatment Periods of the study.

The investigator (and designee) is responsible for ensuring that the specified training for completion of the diary is followed for all subjects/caregivers. Training materials will be provided for site staff and caregiver/subjects. During the study, the investigator will review the subject's progress at the time of a subject's study visit.

# 6.1. Screening Visit (Days -14 to -1)

During the Screening Visit subjects and caregiver(s) will be assessed for study eligibility. This period may last up to 14 days before entering the Treatment Period; however, subjects are encouraged to be screened as soon as conveniently possible to expedite the conversion/titration process. During this visit, the following assessments and procedures will be performed:

- Informed Consent/Assent: Subject's parent or legal guardian must sign the informed consent document (ICD). A subject will be required to provide assent in compliance with local regulations and IRB requirements.
- **Inclusion/Exclusion Criteria:** Assess subject against inclusion and exclusion criteria in Sections 4.1 and 4.2, respectively.
- **Demographics:** Information such as date of birth, race, gender, height, and weight will be collected.
- **Medical History:** Review any significant medical/surgical histories and concurrent illnesses that required or are requiring specialist consultation or treatment.
- **Review Pre-study Opioid Therapy:** Review standard of care opioid therapy and document name, dose, and dosing frequency on the appropriate CRF.
- Concomitant Medications: Record all previous (within last 30 days) and concurrent medications (Over-The-Counter or prescribed): Section 5.7.

- Physical Examination: See Section 7.2.6.
- Clinical Laboratory Testing: Hematology, blood chemistry, and urinalysis (Section 7.2.3).
- **Pregnancy Test:** Conduct serum pregnancy test for all females of childbearing potential (See Section 7.3).
- Urine Drug Test: See Section 7.2.7.
- Electrocardiogram: See Section 7.2.4.
- Vital Signs: Resting blood pressure, pulse rate, and respiration (See Section 7.2.2).
- Suicide Ideation and Behavior (SIB) Assessment: C-SSRS (Section 7.4.1):
  - Children's Lifetime/Recent (Ages 7-11) (Version 6/23/10) Appendix 3.
  - Baseline/Screening (Ages 12-17) (Version 1/14/09) -Appendix 4.
- **COWS:** See Section 7.2.5.
- Adverse Events: Reporting of serious adverse events (See Section 7.2.1).
- Advise the caregiver that the next visit (Visit 2) is the first dose visit with PF-06412528 and request their child refrain from taking their standard of care opioid on the day of Visit 2. In the event the standard of care opioid has been taken, reschedule the visit for the next day. A telephone call is encouraged the day before Visit 2 to remind the caregiver.

#### 6.2. Treatment Period

The Treatment Period will consist of two phases, the Conversion/Titration Phase and the Maintenance Phase. The procedures for each phase are described below.

#### 6.2.1. Conversion/Titration Phase

### Pre-Dose Visit 2 (Day 1)

During this visit (Study Day 1) the following procedures will be followed before the administration of study medication:

- Review any results from laboratory samples (hematology, chemistry, urinalysis, pregnancy tests) that may exclude a subject from participating.
- **Pregnancy Test:** Take a urine sample from all females of childbearing potential.
- Vital Signs.

- SIB Assessment: C-SSRS (Section 7.4.1):
  - Children's Since Last Visit (Ages 7-11) (Version 6/23/10)-(Appendix 5).
  - Since Last Visit (Ages 12-17) (Version 1/14/09)-(Appendix 6).
- COWS assessment.
- **Opioid Therapy Review:** Review standard of care opioid therapy and document name of all opioids, dose, and dosing frequency.
- Concomitant medications: Review and document concomitant medication use (name, dose, and frequency).
- Adverse Event Assessment with focus on serious: Only pre-dose serious adverse events will be documented.
- Pain Intensity: In-clinic assessment.
- Discontinue previous standard of care opioid therapy as part of dose conversion.
- Prescribe Rescue Medication (if needed): Prescribe rescue medication (acetaminophen and/or NSAID's) to be used during conversion and titration. IR morphine may also be prescribed for rescue, with the intent to limit its use until a stable dose is achieved.
- **Dispense Study Drug:** Dispense appropriate dose of PF-06412528 based on the **Conversion Guide** (as described in Appendix 2).
- Caregiver(s) Training and Subject Instruction: Train the caregiver(s) and instruct the subject on study medication administration and recording of drug accountability, including recording the date/clock time of study drug administration, rescue medication use, analgesia assessments and adverse events between visits in the diary.
- Schedule the Visit 3a (Day 7±2 days) visit.

# Visit 3a (Day 7 ±2 Days)

All subjects will have this Day 7 visit, which is designated Visit 3a on the Schedule of Activities.

During this visit, the investigator will review the subject's Daily Diary to assess the subject's pain management to determine whether a stable dose of PF-06412528 has been achieved; ie, a dose that provides adequate analgesia, minimal adverse reactions.

During this visit the following procedures will be followed:

# • Assess Treatment Response:

- Pain intensity (Diary Review and in-clinic assessment);
- Rescue Medication (Diary Review);
- Concomitant Medication (Diary Review);
- Study Drug Use (Diary Review);
- Adverse Events (Diary Review).
- COWS Assessment.
- Concomitant Medication Assessment.
- Adverse Event Assessment.
- **Pregnancy Test:** Take a urine sample from all females of childbearing potential.
- **Vital Signs:** Record blood pressure, pulse rate, and respiration.
- SIB Assessment: C-SSRS (Section 7.4.1):
  - Children's Since Last Visit (Ages 7-11) (Version 6/23/10)-(Appendix 5).
  - Since Last Visit (Ages 12-17) (Version 1/14/09)-(Appendix 6).
- Drug Accountability: See Section 5.6.
- **Dose Titration:** Adjust PF-06412528 dosage as needed to optimize pain therapy.
- **Prescribe Rescue Medication (if needed):** Prescribe rescue medication (acetaminophen and/or NSAID's) to be used during conversion and titration.
- **Dispense Study Drug** (PF-06412528) to caregiver.

**For Converted Subjects:** If, at this visit, the subject has been fully discontinued from the standard of care opiate therapy and successfully titrated to a stable dose of PF-06412528 and with infrequent use of IR morphine for rescue the subject may be scheduled for the next visit, which will be Visit 4 (Schedule of Activities). It is at this visit (Visit 3a) the subject enters the Maintenance Phase of the Treatment Period.

**For Non-Converted Subjects:** If, at this visit, the subject **has not** achieved a stable dose of PF-06412528, this subject will remain in the Conversion/Titration Phase, therefore:

# Final Protocol Amendment 2, 26 May 2015

ADDITIONAL TITRATION VISITS IF NEEDED

### Visit 3b (Day $14 \pm 2$ days)

• Follow the same procedures and assessments as described at Visit 3a.

**For Converted Subjects:** If, at this visit, the subject has been fully discontinued from the standard of care opiate therapy and successfully titrated to a stable dose of PF-06412528 and with infrequent use of IR morphine for rescue the subject may be scheduled for the next visit, which will be Visit 4 (Schedule of Activities). It is at this visit (Visit 3b) the subject enters the Maintenance Phase of the Treatment Period.

**For Non-Converted Subjects:** If, at this visit, the subject **has not** achieved a stable dose of PF-06412528, this subject will remain in the Conversion/Titration Phase, therefore:

• Schedule the Visit 3c (Day 21 ±2) visit.

### Visit 3c (Day 21 ±2 days)

• Follow the same procedures and assessments as described at Visit 3a.

**For Converted Subjects:** If, at this visit, the subject has been fully discontinued from the standard of care opiate therapy and successfully titrated to a stable dose of PF-06412528 and with infrequent use of IR morphine for rescue the subject may be scheduled for the next visit, which will be Visit 4 (Schedule of Activities). It is at this visit (Visit 3c) subject enters the Maintenance Phase of the Treatment Period.

**For Non-Converted Subjects:** If, at this visit, the subject **has not** achieved a stable dose of PF-06412528, the subject will remain in the Conversion/Titration Phase, therefore:

• Schedule the Visit 3d (Day 28 ±2 days) visit.

### Visit 3d (Day $28 \pm 2$ days)

• Follow the same procedures and assessments as described at Visit 3a.

**For Converted Subjects:** If, at this visit, the subject has been fully discontinued from the standard of care opiate therapy and successfully titrated to a stable dose of PF-06412528 and with infrequent use of IR morphine for rescue the subject may be scheduled for the next visit, which will be Visit 4 (Schedule of Activities). It is at this visit (Visit 3d) subject enters the Maintenance Phase of the Treatment Period

**For Non-Converted Subjects:** If, at this visit, the subject **has not** achieved a stable dose of PF-06412528, the subject will be discontinued from treatment. PF-06412528 will be discontinued and if needed, converted to a standard of care analgesic therapy at the investigator's discretion.

- Schedule the Visit 6/Early Termination Visit: See Section 6.3.
- Schedule the Post Treatment/End of Study (Visit 7): See Section 6.4.

#### 6.2.2. Maintenance Phase

Once the investigator has determined that the subject has achieved a stable dose of PF-06412528, the subject will enter the Maintenance Phase of the Treatment Period and scheduled to return in two weeks for Visit 4. In the event a subject prematurely withdraws before Visit 4, perform the Visit 6/ET procedures a soon as possible.

### Visit 4

Perform the following assessments:

- Follow the same procedures and assessments as described at Visit 3a.
- Obtain Plasma Samples: Obtain 2 separate 6 mL blood samples for measurement of the concentration of morphine and metabolites in plasma and naltrexone and 6-β-naltrexone in plasma, with at least 2 hours separating the 1st and 2nd samples.

Record the following items on the appropriate CRF:

- The exact dosing date and clock times of the morning dose and previous 3 doses of PF-06412528, and
- The exact clock time of the blood draw for the 2 samples.

### Visit 5

• Follow the same procedures and assessments as described at Visit 3a.

#### Visit 6/Early Termination

During this visit the following procedures will be followed for all subjects:

- Physical examination.
- Serum pregnancy test.
- Clinical Laboratory Test (Hematology, blood chemistry and urinalysis): See Section 7.2.3.
- Follow the same procedures and assessments as described at Visit 3a, (except do not perform the urine pregnancy test, instead a serum pregnancy test should be performed at this visit): See Schedule of Activity and Section 7.3.

- Obtain plasma samples for PK analysis (only if not acquired at Visit 4): Record the following items on the appropriate CRF:
  - The exact dosing date and clock time for the morning and previous 3 doses of PF-06412528, and
  - The exact clock time of the blood draw for the 2 samples.
- Subjects who discontinue early from the study as well as subjects who complete 2 weeks of PF-06412528 during the Maintenance Phase and have their last dose of PF-06412528 at Visit 4 will complete the Visit 6/Early Termination procedures without the need to return for the Post Treatment/End of Study Visit.
- Schedule Post Treatment/End of Study Visit, if required.

# **6.3. Early Termination Visit**

Subjects who do not reach a stable dose at Visits 3a-3d will proceed to the Early Termination Visit. Subjects who do not complete 2-weeks of the PF-06412528 treatment at their maintenance dose for any reason will proceed to the Early Termination Visit.

All subjects including subjects who discontinue early from the study will complete the procedures specified for Visit 6/Early Termination (see Section 6.2.2).

### 6.4. Post Treatment/End of Study (EOS) Visit 7

Approximately 1 week after discontinuing PF-06412528 and initiating dose conversion back to the subject's standard of care therapy, subjects will undergo the Post-Treatment/End of Study procedures, which will consist of an assessment of any **AEs** since the previous visit and the **suicidality assessment**.

The following procedures will include:

- SIB Assessment: C-SSRS (Section 7.4).
- AE assessment.

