# **SCHEDULE OF ACTIVITIES**

The Schedule of Activities table provides an overview of the protocol visits and procedures. Refer to STUDY PROCEDURES and ASSESSMENTS sections of the protocol for detailed information on each procedure and assessment required for compliance with the protocol.

The investigator may schedule visits (unplanned visits) in addition to those listed on the schedule of activities, in order to titrate study drug or conduct evaluations/assessments required to protect the wellbeing of the subject.

Periods		Screening	eening Treatment								
		(2 Wks)	Conversion/Titration Phase (1 to 4 Wks)					Ma	Follow Up//EOS (Clinic) (1 Wk)		
its	Visit	1	2	3a 	3b 	3c 	$3d^2$	4	5	6/ET	7
Scheduled Visits	Day ±Allowable Window	-14 to -1	1	7±2	NR	NR	NR	21±2	35±2	49±2	56±2
Inled					14±2	NR	NR	28±2	42±2	56±2	63±2
ched						21±2	NR	35±2	49±2	63±2	70±2
Š							28±2	42±2	56±2	70±2	77±2
	Activities										
Informed Consent/Assent 		X									
Inclus	sion/Exclusion Criteria (Sections 4.1 and 4.2)	X									
Demo	ographics	X									
Medi	cal History	X									
Opioi	d Therapy Review	$x^4$	$X^{5}$								
	Physical Examination (Section 7.2.6)	X								X	
	Clinical Laboratory Tests (Section 7.2.3)	X								X	
8.	Pregnancy Test (Section 7.3)	$X^{6}$	<				X 		>	$X^{6}$	
Safety	Urine Drug Test (Section 7.2.7)	X									
N	Single, 12–lead ECG  (Section 7.2.4)	X									
	Vital Signs (Section 7.2.2)	X	X	X	X	X	X	X	X	X	
	Suicide Ideation and Behavior (SIB)	X	X	X	X	X	X	X	X	X	X

Periods		Screening Treatment									Post-Treatment
		(2 Wks)	Conversion/Titration Phase (1 to 4 Wks)					Ma	Follow Up//EOS (Clinic) (1 Wk)		
its	Visit	1	2	3a 	3b 	3c 	3d 	4	5	6/ET	7
Scheduled Visits	Day ±Allowable Window	-14 to -1	1	7±2	NR	NR	NR	21±2	35±2	49±2	56±2
nled					14±2	NR	NR	28±2	42±2	56±2	63±2
pəq						21±2	NR	35±2	49±2	63±2	70±2
S							28±2	42±2	56±2	70±2	77±2
	Activities										
	Assessment (Section 7.4.1)										
	COWS (Section 7.2.5)	X	X	X	X	X	X	X	X	X	
	Concomitant Medication (Section 5.7)	X	X	X	X	X	X	X	X	X	
	Adverse Events  (Section 7.2.1)	X	X	X	X	X	X	X	X	X	X
	Pain Intensity (In-Clinic) (Section 7.1.1)		X	X	X	X	X	X	X	X	
Treatment Response	Review Diary Information 11			X	X	X	X	X	X	X	
odsa	Pain Intensity (Diary Review)			X	X	X	X	X	X	X	
t Re	Rescue Medication (Diary Review)			X	X	X	X	X	X	X	

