# 3.2.2. Maintenance Phase (Visit 4-6)

The goal of the Maintenance Phase is to characterize the PK under steady-state study conditions as well as demonstrate the safety of PF-06412528 over a 2-6 week period. If at Visit 4 subjects require additional pain relief in the opinion of the investigator, they will continue in the study for an additional 2-4 weeks (Visit 5 and/or Visit 6) up to 6 weeks total.

Daily Diary and in-clinic pain intensity and safety will be assessed at each visit to determine if any dose adjustments are required. Rescue medication (acetaminophen and/or NSAID's) is permitted during this phase. IR morphine for rescue is discouraged during the Maintenance Phase.

Blood samples will be collected for PK analysis at Visit 4 for those subjects that achieve a stable dose between Visits 3a-d. Two blood samples will be taken at least two-hours apart at Visit 4. If for any reason PK samples are not obtained at Visit 4, the subject should return to enable them to be obtained at an unscheduled visit.

At the final Maintenance Phase visit (Visit 4 or 5 or 6), the investigator will discontinue the subject's PF-06412528 therapy and convert the subject back to their standard of care of opioid therapy. Blood samples will be collected for PK analysis if not already obtained. A Post-Treatment/End of Study visit will be scheduled in 7 ±2 days (Visit 7).

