# 3.3. Post-Treatment Period/End of Study Period

The purpose of the Post-Treatment Period/End of Study (Visit 7) is to perform safety assessments  $7 \pm 2$  days after the last dose of PF-06412528 at Visit 6.

Subjects who discontinue early from the study as well as subjects who complete 2 weeks of PF-06412528 during the Maintenance Phase and have their last dose of PF-06412528 at Visit 4 will complete the Visit 6/Early Termination procedures without the need to return for the Post Treatment/End of Study Visit.

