### 7.1. Analgesic Effect Assessments

### 7.1.1. Pain Intensity

Daily average NRS-Pain scores will be assessed with an 11-point NRS ranging from zero (no pain) to 10 (worst possible pain) captured on the diary (Appendix 7). A subject will rate their average pain intensity during the past 24 hours by choosing the appropriate number from 0 to 10 as shown below. The subject will conduct the self-assessment daily with the caregiver(s) in the evening prior to bedtime and recorded in the diary during the Treatment and Post-Treatment Periods. These diary assessments will be reviewed by the investigator at the in-clinic visits for the purpose of assessing the need for titrating study drug and will not be documented. Pain Intensity will also be completed at the in-clinic visits during the Treatment and Post-Treatment Periods. Only the in-clinic visit pain assessments will be documented for analysis.

Select the number that best describes your average pain in the past 24 hours. (Select one number only).

0	1	2	3	4	5	6	7	8	9	10
No										Worst
Pain										Possible Pain

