#### 9.4.1. Adverse Events

All AEs will be coded to System Organ Class and Preferred Term (using MedDRA®). Treatment-emergent AEs will be defined as AEs that commence on or after the start of PF-06412528 administration. Subjects who have multiple events in the same System Organ Class and Preferred Term in a period will be counted only once at each level of summation (overall, by System Organ Class, and by Preferred Term).

Treatment-emergent AEs will be summarized separately for the Conversion/Titration Phase and the Maintenance Phase (including up to End of Study) by System Organ Class, Preferred Term, maximum intensity, and highest relationship to study drug.

Serious AEs and those leading to study withdrawal will be summarized.

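### Children who finish PF-06412528 at Visit 5 or 6 have no scheduled COWS or vital signs after the switch back to standard-of-care opioid, and AEs from that week are tabulated as Maintenance

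*Protocol*

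**What the plan says.** At the final Maintenance visit, which Protocol 3.2.2 allows to be Visit 4, 5 or 6, "the investigator will discontinue the subject's PF-06412528 therapy and convert the subject back to their standard of care of opioid therapy". The same section continues: "A Post-Treatment/End of Study visit will be scheduled in 7 ±2 days (Visit 7").

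Protocol 3.3 gives the reason for that visit: "The purpose of the Post-Treatment Period/End of Study (Visit 7) is to perform safety assessments". Its content is narrow. Section 6.4 times the visit "Approximately 1 week after discontinuing PF-06412528 and initiating dose conversion back to the subject's standard of care therapy", and at that point "subjects will undergo the Post-Treatment/End of Study procedures, which will consist of an assessment of any" AEs, plus the C-SSRS. The Schedule of Activities agrees: COWS, vital signs and in-clinic pain are marked through Visit 6/ET and blank at Visit 7.

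Section 7.1.1 differs on pain: "Pain Intensity will also be completed at the in-clinic visits during the Treatment and Post-Treatment Periods". It adds that only in-clinic scores, not diary scores, are kept for analysis.

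For reporting, Protocol 9.4.1 and SAP 8.1.4 split treatment-emergent AEs into Conversion/Titration and "the Maintenance Phase (including up to End of Study"). COWS and vital signs are summarised by visit (Protocol 9.4.4 and 9.4.5). Pain is summarised by week and phase of the Treatment Period (Protocol 9.2).

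**The concern.** Symptoms of opioid toxicity or withdrawal are part of the primary safety endpoint (Protocol 2.2.1), and respiratory rate belongs to a secondary one (2.2.2). COWS is the instrument chosen for objective signs of withdrawal. A change of opioid is an occasion on which these measures are informative, and the protocol schedules them around the first change, at Visit 2 and weekly through titration. For the change back, a child finishing at Visit 5 or 6 has none scheduled afterwards. The conversion guide in Appendix 2 also says that its ratios are not to be used in reverse, so it does not cover this switch.

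Two things are at stake. A withdrawal-type or sedation-type AE in that week has no scheduled objective reading beside it. The event is also tabulated under Maintenance, so a reader could take it as arising on a stable dose of PF-06412528 when the child was already on another opioid.

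**Working it through.** **1. The interval.** From the Schedule's four tracks, Visit 7 minus Visit 6 is 56−49, 63−56, 70−63 and 77−70, which is 7 days each time. This reproduces the stated 7 ±2 days, a range of 5 to 9. If only the two calendar windows in the Schedule were applied (±2 each), the gap could run from 7−4 = 3 to 7+4 = 11 days.

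**2. Scheduled assessments, counted over the Schedule's ten visit columns.**

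| Measure | Through Visit 6/ET | At Visit 7 |
|---|---|---|
| COWS | 9 | 0 |
| Vital signs | 9 | 0 |
| In-clinic pain | 8 | 0 (7.1.1 says otherwise) |
| AEs | 9 | 1 |
| C-SSRS | 9 | 1 |

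These are column counts. A child stable at Visit 3a who finishes at Visit 6 has COWS at Visits 1, 2, 3a, 4, 5 and 6, so 6 readings, all at or before the stop.

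**3. Scheduled frequency of COWS and vital signs.** Titration visits are 7 days apart, or 1.0 per week. Maintenance visits are 14 days apart, or 0.5 per week. From the last dose to Visit 7 there are 0 in about 1 week.

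**4. Can the Visit 6 reading stand in?** Protocol 3.3 puts the last dose at Visit 6, and 5.1.3 says the capsule goes on releasing morphine for up to 24 hours. A reading taken that day cannot show the effect of the switch.

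**5. Pain passages side by side.** Section 7.1.1 includes the Post-Treatment Period for in-clinic pain. The Schedule and section 6.4 have no such score at Visit 7, the only Post-Treatment visit. Diary entries continue after treatment, but the Schedule has no diary review at Visit 7 and diary pain is not analysed.

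**6. Weight of the off-drug week in the Maintenance AE column.** Maintenance runs from the visit at which the dose is stable. On the first track that is 49−7 = 42 days to Visit 6 and 35−7 = 28 days to Visit 5. The share is off-drug days ÷ (Maintenance days + off-drug days):

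- Visit 6 finisher: 7/(42+7) = 14.3%; range 5/47 = 10.6% to 9/51 = 17.6%.
- Visit 5 finisher: 7/(28+7) = 20.0%; range 5/33 = 15.2% to 9/37 = 24.3%.

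These are shares of time, not of events. They use the protocol's End of Study at Visit 7. SAP 2.1 still describes a later End of Study visit 28 ±2 days after the last dose, which would lengthen the off-drug part.

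**7. Children outside this group.** A child not stable at Visit 3d stops the drug and then has the Visit 6/ET visit scheduled (6.2.1), so can have all three measures after stopping. Early discontinuers and Visit 4 finishers complete Visit 6/ET procedures and are excused from Visit 7 (3.3, 6.2.2).

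**The case against.** The best defence is that a short follow-up visit is a legitimate design choice. The primary safety endpoint is worded as AEs during treatment with PF-06412528, and a COWS taken a week into another opioid is not needed for it. COWS records what is present at the assessment, so one reading at day 7 ±2 may miss early withdrawal and could falsely reassure. COWS and vital signs are already summarised by visit, so any Visit 7 value would appear on its own row. All of this stands, and it limits what the added measures can deliver. It does not explain why off-drug AEs share a column with Maintenance; the endpoint's own wording argues for separating them. Nor does it resolve the contradiction over pain.

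A reader might also infer more than the documents support:

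- **That this week carries the main risk.** No passage ranks it above the initial conversion. The withdrawal risk named in Protocol 1.6 is tied to the formulation.
- **That COWS covers only time when withdrawal is unlikely.** It is scheduled at Visit 2, when the earlier opioid is stopped, and weekly through titration, after a starting dose that section 5.4 generally halves.
- **That events surface only if volunteered.** Section 8.13 requires questioning about AEs. Caregivers are trained on toxicity and withdrawal signs, keep a diary and are contacted at least weekly (4.4, 7.2.1.2).
- **That no child can have these measures after stopping.** Visit 3d failures can. An unscheduled AE visit also requires Visit 6/ET procedures (6.7), although that section does not say whether this extends to the Post-Treatment Period.

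**Conclusion.** The point holds in a limited form, as a gap in objective measurement and a reporting weakness, with one internal contradiction. For Visit 5 and Visit 6 finishers, scheduled COWS and vital signs after the switch number zero over a nominal 7 days. The AEs of that week enter a Maintenance column in which off-drug time is nominally 14% to 20% of the period covered. Section 7.1.1 must be reconciled with the Schedule and section 6.4 on Visit 7 pain.

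This assumes that a Visit 5 finisher has the closing assessments at Visit 5 and then attends Visit 7. Section 3.2.2 implies this, but the protocol spells out the closing procedures only for Visit 4 finishers. The documents do not say how many children will finish at Visit 5 or 6, so the number affected could be anywhere from none to all of the 100 or more expected to complete two weeks of Maintenance. No hypothesis test or sample-size figure is affected. Nothing here shows that withdrawal is being missed, only that any that occurs would have no scheduled objective measure beside it.

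**What to change.** - In the Schedule and section 6.4, add COWS, vital signs (respiratory rate, pulse, blood pressure) and the in-clinic NRS to Visit 7, which the Schedule already lists as a clinic visit. This brings both into line with section 7.1.1.
- Label those values Post-Treatment in Protocol 9.2, 9.4.4 and 9.4.5 and in the matching SAP sections (8.3, 8.1.7, 8.1.8).
- In Protocol 9.4.1 and SAP 8.1.4, show AEs that start after the last dose in a separate Post-Treatment column and remove them from Maintenance. This is worth doing even if no assessment is added.
- Reconcile who attends Visit 7. Protocol 3.3 and 6.2.2 excuse early discontinuers and Visit 4 finishers, the Visit 3d text in 6.2.1 schedules the visit for children not stabilised, and SAP 2.1 requires it of all treated subjects.

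The cost is an estimated 10 minutes of existing staff time per attending child, some Schedule wording and one more table column. Two limits should be stated in the report: a single reading at day 7 ±2 can miss early withdrawal, and the change does not reach children excused from Visit 7.
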